5.3 Concomitant Medications and Treatments

All treatments and drugs used within 1 month prior to signing the informed consent form and in the course of the study should be recorded in the eCRF strictly in accordance with the GCP guideline. If adverse events occur, the subject should be closely observed, as well as given active symptomatic treatment if necessary, and the drug used shall be recorded and specified in the eCRF.

5.3.1 Drugs and therapies prohibited during the study

Subjects are prohibited from using modern traditional Chinese medicines that have been approved by the NMPA (including but not limited to Delisheng Injection, Kanglaite Injection, Aidi Injection, Huaier Granule and Ganfule Tablet) and immunomodulators (including but not limited to interferon, interleukin-2, thymosin, etc.) during the study.

During the treatment period of this study, subjects are not allowed to receive any local therapies against liver lesion and targeted lesion, and other systemic anti-cancer therapies, such as chemotherapy, molecular targeted therapy, hormone therapy, immunotherapies, traditional Chinese medicine therapy (as mentioned above) and radiotherapy.

Subjects are not allowed to receive other immunosuppressive therapy simultaneously during the treatment period of this study (except management on the treatment-related AE).

Investigational drugs for cancer treatment

5.3.2 Permitted concomitant medications and treatments during the study

1. Antiviral treatment

Subjects infected with HBV and HCV must receive antiviral therapy according to local standards, and the antiviral therapy is recommended as below:

Subjects with HBV infection can continue the original antiviral therapy if HBV-DNA is positive and they have started antiviral therapy and achieved satisfactory control of virus (HBV-DNA < 500 IU/mL) prior to inclusion in the study; the drug must be replaced by Entecavir if the virus is not satisfactorily controlled, and subjects can be enrolled when HBV-DNA is < 500 IU/mL; subjects with newly discovered HBV infection in screening period can start Entecavir therapy immediately and can be enrolled when HBV-DNA is < 500 IU/mL.

Subjects with HCV infection, if HCV-RNA is positive, subjects must receive antiviral therapy in accordance with the local standard guideline on diagnosis and treatment of hepatitis C.

2. Steroids

Local use of steroids is allowed, for example, topically external use, eye, nasal cavity, intra-joint and inhalation; corticosteroids for epinephrine replacement therapy are allowed; corticosteroids for treatment of adverse reactions are allowed; transient use of steroids for prevention and treatment of allergic reactions (prevention of allergy to contrast agent, or treatment of other allergic reactions) is allowed.

3. Vaccines

Vaccines for preventing infectious disease are allowed, for example, pneumonia or influenza vaccines. It must be discussed with the sponsor before using other vaccines.

4. Other systemic therapies

During the treatment period, subjects should be given the best supportive treatment. The original hormone replacement therapy is allowed. Bisphosphonate for treatment of bone metastasis is permitted.

5. Palliative local treatment

Palliative therapy for local lesions causing obvious symptoms is allowed, for example, bone pain; local radiotherapies or surgery can be considered, however, the following conditions must be met:

Progression of disease must be judged by investigators for subjects who need local therapy due to deterioration of symptoms during the study;

Subjects with disease progression must meet the criteria for treatment beyond progression (see Section 3.2.4);

The lesions for local therapy cannot be target lesions.

It is advisable to discuss with the sponsor prior to the start of palliative local therapy. The content of palliative therapy should be recorded carefully in eCRF and medical record, including the date, site of treatment, therapeutic method and dosage, adverse reactions, and so on.

5.4 Criteria for Re-screening of Subjects

Rescreening is allowed in this study, i.e., subjects who have entered screening process but do not meet randomization criteria, and have not been randomized or treated, can be re-enrolled. They must sign the informed consent form again, and obtain a new subject number at the time of re-screening.

5.5 Criteria for Subjects' Withdrawal from the Study or Termination of Study Treatment

Subjects must terminate study treatment when any of the following conditions occurs:

1. Subject withdraws informed consent and requires to withdraw from the study.
2. Medical imaging examination shows progression of disease, unless the subject meets the criteria on post-progression continuation of therapy (see Section 3.2.4);
3. Occurrence of clinical adverse events, abnormal laboratory examination or co-morbidities occur, when continued participation in the study is judged by investigators as violating the subject's optimal benefit;
4. Other reasons for inability to continue study treatment, as considered by investigators, for example, loss of the ability to express wills freely for custody or isolation;
5. Pregnancy in female subject occurs during the study;
6. Termination of study by sponsor.

5.6 Criteria for Termination of Study Treatment

The criteria for study termination are as follows:

(1) Criteria for terminating treatment at study site:

If the sponsor discovers a serious or persistent non-compliance with the protocol and other trial procedures in study sites, the sponsor will have the right to suspend the trial conducting at the study site. In this case, the sponsor will immediately inform the investigator and the regulatory authorities of the termination information. The investigator must immediately report this termination information to the ethics committee and provide corresponding reasons.

If the investigators terminate or suspend the trial in study site, they must inform subjects immediately and report the written decision to the sponsor and the regulatory authority, as required by regulations, and state the reason. The investigator should also report promptly to the ethics committee and the clinical trial institution, and state the reason.

(2) Criteria for terminating the entire study:

The study can be terminated or interrupted prematurely if the reason is sufficient. If the study is terminated or interrupted in advance, the sponsor shall provide a written notice which records the reasons for early termination or interruption to investigators, the National Medical Products Administration and relevant departments. The principal investigator should notify the ethics committee and the sponsor immediately, and provide relevant reasons.

The reasons for premature termination or interruption of the study may include (but not limited):

- Discovery of unexpected, significant or unacceptable risk;
- Major mistakes in the protocol are found during the trial;
- Ineffective investigational drug/trial therapy, or meaningless to continue the study;
- The enrollment of subjects is seriously prolonged or having frequent protocol deviation, which makes it extremely difficult in completing the study.

5.7 Subject ID

Subjects will be assigned a unique number in the study with five digits:

- The first 2 digits = Site number.
- The last 3 digits = Subject number in the same site. The subjects will be numbered in accordance with the sequence in which the subjects sign the informed consent form, for example: 001, 002, 003, etc.

6 STUDY TREATMENT

6.1 Information of Investigational Drug

Investigational drug: SHR-1210 for injection

Manufacturer: Shanghai Hengrui Pharmaceutical Co., Ltd., Suzhou Shengdia Biological Medicine Co., Ltd.

Dosage form: lyophilized powder

Specification: tentatively set as 200 mg and packed in 20 ml vials. The batch number is provided in the drug inspection report in detail;

Administration: intravenous infusion;

Shelf life: 2 years (tentative) from the date of manufacture;

Storage: Stored in sealed, protected from light, stored in a medical refrigerator at 2–8°C, must not be frozen.

6.2 Drug Dispensation

Management, dispensation and return of the investigational drugs in this study will be performed by a special person, investigators must make sure all the investigational drugs are only used for the subjects in this clinical trial, the dosage and administration method should be in accordance with the protocol, the residual investigational drugs will be returned to the sponsor and must not be transferred to any non-clinical trial participant.

The investigational drugs are stored in a medical refrigerator at 2–8 °C. When the drug is dispensed to the study site, a drug receipt form must be signed by two persons in duplicate, one for clinical study site and the other for sponsor. At the end of the study, the remaining drugs and empty boxes will be returned, and the two sides need to sign a drug return form. The dispensation and return of each drug shall be recorded on a specific record sheet in time.

Monitors are responsible for monitoring supply, use, storage of the investigational drugs and treatment of the remaining drugs.

6.3 Drug Storage and Management

In accordance with the requirement of the GCP, the investigational drugs are uniformly stored, dispensed and returned by the participating study site. The investigational drugs should be sealed and protected from light, stored in a medical refrigerator at 2–8 °C, and must not be frozen.

SHR-1210 is not permitted to be used in the treatment outside of this study.

6.4 Disposal of Remaining Drugs

Investigators should record the date and dose of the drug administered for each subject. The total amount of investigational drugs is 110% of the designed amount, and the residual investigational drugs will be returned to the sponsor regularly for destruction after being counted. If the remaining drugs should be destroyed at study sites, the written certification of the destruction of residual investigational drugs needs to be obtained and stored as well.

6.5 Dose Regimen

The subjects randomized to Group A will receive SHR-1210 3 mg/kg intravenous infusion over 30 minutes (no less than 20 minutes and no more than 60 minutes, including a wash-out period) once every two weeks. The subjects randomized to Group B will receive the same dose once every three weeks.

The interval between two doses cannot be less than 12 days for once every two weeks. The interval between two doses cannot be less than 18 days for once every three weeks.

6.6 Common Recommendations on Safety Management

6.6.1 Infusion reaction

As SHR-1210 is a fully humanized monoclonal antibody, the possibility of infusion or allergic reaction is low, and preventive medication is not needed prior to infusion. Allergic reaction is most likely to occur within 24 hours after infusion. Once the allergic reactions occur, the infusion should be slowed down or interrupted based on the condition, and clinical supportive treatment is needed, and after that, the preventive medication should be given prior to the subsequent doses.

The allergic reactions are possibly characterized by fever, intolerance of cold, chills, headache, rash, pruritus, joint pain, low or high blood pressure, or bronchospasm. All the Grade 3 or 4 infusion reactions should be reported to the sponsor within 24 hours, and reported as SAE in case of meeting the criteria for SAE. See detailed reporting method in Section 9.2.

Response to allergic reactions should be based on the medical practice and guidelines of the study site. The following is the recommendations for the treatment of infusion reaction for reference.

Table 4 Recommendations on management of immune related adverse reactions

CTCAE Grade	Clinical symptoms	Clinical treatments	SHR-1210 treatment
Grade 1	Mild transient reactions	Bedside monitor, close monitoring till recovery. Preventive medication is recommended prior to the infusion afterwards: Diphenhydramine 50 mg, or equivalent and/or Acetaminophen 325–1000 mg, administered at least 30 minutes before the infusion of SHR-1210.	Continue.
Grade 2	Moderate reaction requiring treatment or dose interruption that can be rapidly relieved after symptomatic treatment (e.g., antihistamine drugs, non-steroid anti-inflammatory drugs, anaesthetics, bronchodilator, intravenous infusion, etc.)	Normal saline i.v. infusion, Diphenhydramine 50 mg i.v. or equivalent and/or Acetaminophen 325–1000 mg; bedside observation, close monitoring till recovery. Corticosteroid or bronchodilator can be considered if clinically required; The dose of investigational drug administered will be recorded in the source documents; Preventive medications are recommended prior to the infusion afterwards: Diphenhydramine 50 mg, or equivalent and/or Acetaminophen 325–1000 mg, administered at least 30 minutes before the infusion of SHR-1210. Cortisol (equivalent to 25 mg hydrocortisone), can be used if necessary.	Interrupted temporarily. Resuming the medication after symptoms disappear at 50% of the initial infusion rate. If there is no complication within 30 minutes, increase to the original 100% infusion rate. Closely monitor. If relapse, the current dose of SHR-1210 cannot be given again.
Grade ≥ 3	Grade 3: serious reaction, no rapid relief after treatment and/or dose interruption; or relapse after remission; sequela occurred requiring hospitalization. Grade 4: life threatening	The infusion of SHR-1210 shall be immediately discontinued; And normal saline i.v. infusion should be started. 
 Bronchodilator, 0.2–1 mg 1:1000 epinephrine solution (s.c.) , or 0.1–0.25 mg 1:10000 epinephrine solution (i.v.), and/or diphenhydramine 50 mg combined with methylprednisolone 100 mg or equivalent drugs (i.v.) is/are recommended; 	Discontinued permanently.

CTCAE Grade	Clinical symptoms	Clinical treatments	SHR-1210 treatment
		
 Comply with guidelines for allergic reactions of the study site; Bedside monitor, close monitoring, till recovery. 	

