7.2.4 Criteria for permanent treatment discontinuation

The study medication must be discontinued permanently when the following conditions occur:

- Any Grade 2 treatment-related uveitis, ophthalmodynia, and blurred vision, that has no response to local therapy and is not recovered to Grade 1 after delayed dose; or the above AE requiring systemic therapy.

- Any Grade 3 treatment-related non-cutaneous AE, lasting for > 7 days, except the following:
 - When any Grade 3 treatment-related uveitis, pneumonia, bronchospasm, hypersensitivity, or infusion reaction occurs, the study treatment must be terminated;
 - In case the Grade 3 treatment-related endocrine disorder can be sufficiently controlled only with hormone replacement therapy at physiological dose, the treatment does not need to be terminated;
 - The treatment does not need to be terminated for Grade 3 treatment-related laboratory abnormality, however, the study medication must be terminated for Grade 3 thrombocytopenia > 7 days or related with hemorrhage.
- Hepatotoxicity meeting the following:
 - AST or ALT > 10 times of ULN for over two weeks;
 - ALT or AST > 15 × ULN;
 - TBIL > 8 times of ULN for subjects with elevated TBIL at baseline, > 5 times of ULN for subjects with normal TBIL at baseline;
- Any Grade 4 treatment-related AE or abnormal laboratory examination, except the following:
 - Grade 4 granulocyte decrease lasts less than 7 days;
 - Grade 4 lymphopenia or leukopenia;
 - Isolated Grade 4 elevated amylase or lipase, without symptoms or clinical manifestations of pancreatitis. The sponsor needs to be informed in case of Grade 4 elevated amylase or lipase occurs;
 - Isolated Grade 4 electrolyte imbalance/abnormality without clinical sequela that could be corrected through supplement/appropriate management within 72 hours after occurrence;
 - Grade 4 treatment-related endocrine disorder that can be sufficiently controlled only with hormone replacement therapy at physiological dose, the treatment does not need to be terminated.

- The study treatment must be terminated in case dose delay > 6 weeks is required, except the following:

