9.4 AEs of Special Interest

For the AE of special interest specified in the clinical study protocol, investigators need to fill in the “Adverse Event of Special Interest Report Form in Hengrui Clinical Study” within 24 hours after awareness, and report to the sponsor.

If it is SAE at the same time, please also fill in “Serious Adverse Event Report Form” and report to the relevant department in accordance with SAE procedure.

- \geq Grade 3 infusion reaction
- \geq Grade 2 diarrhea/colitis, uveitis, or interstitial pneumonia
- \geq Grade 3 other immune-associated adverse events
- Any possible event of abnormal hepatic enzyme (see Section 9.2.3, whilst lacking other related causes, for example, progression of disease, acute viral hepatitis, cholestasis, concomitant medication, pre-existing hepatopathy, etc.)
- Grade 4 increased amylase or lipase

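### In protocol Table 4, an infusion reaction that returns after resumption is handled in the Grade 2 row but, on the most natural reading, also meets the Grade 3 description; the rows must be reconciled

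*Protocol*

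**What the plan says.** **Table 4, Grade 2 row (protocol Section 6.6.1).** The row describes a moderate reaction that settles quickly with symptomatic treatment. The infusion is interrupted, then: "Resuming the medication after symptoms disappear at 50% of the initial infusion rate". If 30 minutes pass without trouble, the full rate is restored. If the reaction comes back: "If relapse, the current dose of SHR-1210 cannot be given again". The treatment column of the same row adds: "Preventive medications are recommended prior to the infusion afterwards".

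**Table 4, Grade ≥ 3 row.** The Grade 3 description opens with a serious reaction that is not rapidly relieved, and continues: "or relapse after remission; sequela occurred requiring hospitalization". The instruction for SHR-1210 is permanent discontinuation.

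**Rules that depend on the grade.**
- Section 7.2.4: "When any Grade 3 treatment-related uveitis, pneumonia, bronchospasm, hypersensitivity, or infusion reaction occurs, the study treatment must be terminated".
- Section 6.6.1: "All the Grade 3 or 4 infusion reactions should be reported to the sponsor within 24 hours".
- Section 9.4 lists ≥ "Grade 3 infusion reaction" as an adverse event of special interest (AESI), with its own 24-hour form. SAP Section 5.5.2 carries the same category into the analysis.

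**Status of the table and source of grades.** Section 6.6.1 introduces Table 4 with: "The following is the recommendations for the treatment of infusion reaction for reference". Sections 9 and 9.1.2 name NCI-CTCAE v4.03 as the grading standard, and the first column of Table 4 is headed as a CTCAE grade.

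**The concern.** The Grade 2 row itself sets up the situation in question: symptoms clear, the infusion restarts, symptoms return. It answers by withholding the current dose and goes no further. The next row appears to place the same sequence of events in Grade 3, with a different consequence for the subject.

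The grade matters beyond the table. It decides whether the mandatory stop in Section 7.2.4 applies, whether the infusion-reaction report is due within 24 hours, and whether the event enters the AESI summary. A site that works from the Grade 2 row could give a further dose to a subject whom Section 7.2.4 would require to stop. The count of Grade ≥ 3 infusion reactions, and the count of subjects who stop treatment for adverse events, could then depend partly on which row a site applied.

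**Working it through.** The plan states no figure on this point, so there is nothing to reproduce. The check sets the provisions side by side.

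**Step 1: define the event.** A subject has a Grade 2 reaction, the infusion is interrupted, symptoms disappear, the infusion restarts at half rate, and the reaction returns.

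**Step 2: compare with the Grade 2 row.** The event fits. Resumption is conditional on symptoms having disappeared, and the row has a specific instruction for relapse. That instruction is confined to the current dose.

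**Step 3: compare with the Grade 3 description.** Because the infusion restarts only after symptoms have gone, a return of the reaction is a relapse after remission in the ordinary sense of the words. The semicolon and the word *or* before that phrase make it most naturally a criterion of its own. The event therefore fits here too.

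**Step 4: compare the consequences.**

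| Consequence | If handled as Grade 2 | If handled as Grade 3 |
|---|---|---|
| Current dose | Not given again | Infusion stopped |
| Later doses | Not expressly addressed after a relapse; premedication foreseen for later infusions; Section 7.2.3 generally allows resumption on recovery to Grade 1 or below, or to baseline | Permanent discontinuation (Table 4) and mandatory termination (Section 7.2.4) |
| Report within 24 hours | Only if the event meets another trigger, such as the SAE criteria (Sections 9.2.1 and 9.2.6) | Yes (Sections 6.6.1 and 9.4) |
| AESI | Not under the infusion-reaction item | Yes (Section 9.4, SAP Section 5.5.2) |

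**Step 5: look for a rule that settles the overlap.** Sections 7.2.2 and 7.2.3 on delay and resumption do not mention relapse during a resumed infusion. Section 9.1.2 points to NCI-CTCAE v4.03, whose text is not in the documents. Neither row of Table 4 tells the site to regrade. No provision in the protocol or SAP expressly assigns the event to one row.

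**Step 6: scale.** The documents give no infusion-reaction rate, and Section 6.6.1 calls the possibility low. Two calculations are possible.
- *Per event.* If all 220 planned subjects are dosed, one event moved between grades shifts the overall AESI rate by 1/220 = 0.45 percentage points. With 1:1 allocation there are 110 subjects per group, and the shift within a group is 1/110 = 0.91 points.
- *Illustration on assumed rates only.* Suppose 5% to 10% of subjects have a Grade 2 reaction: 220 × 0.05 = 11 and 220 × 0.10 = 22. Suppose 10% to 30% of these relapse on resumption: 11 × 0.10 = 1.1 and 22 × 0.30 = 6.6, so about 1 to 7 subjects. If every one of them changed grade, the overall rate would move by between 1/220 = 0.5% and 7/220 = 3.2%. Nothing in the documents supports either assumed range, and a lower reaction rate reduces the count in proportion.

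**The case against.** The strongest reply is that the two rows can both be obeyed in sequence: stop today's dose, regrade the event and, if it is now Grade 3, follow the next row and Section 7.2.4. A reader might infer that the Grade 2 row costs a relapsing subject only the current dose and authorises later ones. The text does not go that far. It bars re-giving that dose, and its premedication advice covers Grade 2 reactions in general. What remains is that the row deals with relapse explicitly and stops short of saying that the event must be regraded or that treatment may have to end.

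Second, the opening reference to a serious reaction may govern the whole Grade 3 entry, so that a moderate return of symptoms stays in Grade 2. This cannot be excluded. The punctuation favours the stand-alone reading, but the text does not settle it, and two tenable readings are enough for sites to differ.

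Third, it would be too strong to say that nothing governs the grade, because the protocol adopts NCI-CTCAE v4.03. This stands. Whether that standard resolves the relapse case cannot be judged from the documents, so divergent grading between sites is a possibility and has not been shown.

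Fourth, Table 4 is advisory and defers to local practice. That is true of the table, but Section 7.2.4 is mandatory, and the 24-hour report and the AESI list also follow the grade.

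Finally, a reader might infer that the Grade 2 route never leads to expedited reporting. It can: an event that meets the SAE criteria goes to the sponsor within 24 hours at any grade.

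**Conclusion.** The point holds as a conflict in wording between the Grade 2 and Grade ≥ 3 rows of Table 4, with binding consequences through Section 7.2.4. It rests on reading relapse after remission as a criterion in its own right, which is the more natural reading but not the only one. The documents do not show that the plan directs re-dosing after a relapse, that sites will in fact act in opposite ways, or that any particular number of subjects is involved.

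The size is unknown. Each event that changes grade moves the overall AESI rate by about 0.45 percentage points if 220 subjects are dosed; the range of 1 to 7 subjects is an illustration on assumed rates and not an estimate. ORR and the 6-month OS rate are not directly affected, and the safety analysis is descriptive. The correction is worth making because the grade decides whether a subject must stop treatment, and because a small AESI count is sensitive to one or two reclassified events.

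**What to change.** Reconcile the Grade 2 and Grade ≥ 3 rows of Table 4 with each other, with Section 7.2.4 and with the NCI-CTCAE v4.03 grading that the protocol adopts, so that a relapse after resumption falls under one row only. State the grade to be recorded in the eCRF for that event, and let the 24-hour report in Section 6.6.1 and the AESI count in Section 9.4 and SAP Section 5.5.2 follow that grade. Which row should apply is a clinical decision for the sponsor and investigators, and no view is taken on it here.

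The cost is a wording change in one table and one line in the eCRF completion guideline, submitted to the ethics committee as Section 12.2 requires for any amendment. No extra subjects or visits are needed.
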